- **Hypothesis 1:** Based on our preliminary data, we hypothesize that MI-consistent therapist behaviors (e.g., reflections) will be associated with greater BOLD response in the medial frontal gyrus (MFG), inferior frontal gyrus (IFG), and insula, as compared with MI-inconsistent therapist behaviors (e.g., confront).

- **Hypothesis 2:** Greater BOLD response (MFG, IFG, insula) will be associated with greater proximal (3-month, 6-month) and distal (12-month) reductions in adolescent problem drinking (frequency of binge drinking, alcohol related problems).

Aim 2: Evaluate whether brain activity mediates therapist language and youth behavior change.

- **Hypothesis 3:** BOLD response (MFG, IFG, insula) will mediate the relationship between MI-consistent therapist behaviors (e.g., reflections) and proximal and distal reductions in adolescent problem drinking.

3) Background

Adolescence is a unique developmental period. Within the United States (U.S.), adolescents are encouraged to begin taking responsibility for more "adult" decisions (e.g., driving, dating, unsupervised social events, which often include alcohol). Yet, the brain regions responsible for weighing consequences, judging costs and benefits, and self-regulating, are still very much in development during this period (Luna et al 2010). This matters because recent human and animal studies suggest that alcohol use during adolescence may be neurotoxic ([name] et al under review-b, Jacobus & Tapert 2013, Spear 2013). Meaning drinking, particularly in high-risk patterns like binge drinking, may negatively influence youths' neurodevelopmental trajectory, subsequently placing youth at greater risk for sustained patterns of alcohol use and related problems as they transition into adulthood (e.g., Luciana et al 2013, Squeglia et al 2012).

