NILE fMRI Task. PI [name] and Co-I [name] have pioneered the examination of within-session factors (client language; therapist language) in the brain. For this study, we will expand upon a task that we have developed and published on, which has empirically shown how salient within-session factors influence the brain and subsequent treatment outcomes ([name] et al 2011b, [name] et al under review-a, [name] et al 2013b, [name] under review). Based on our work with client language (change talk; CT; sustain talk; ST), our fMRI procedure assesses the effects of within-session counselor language on adolescent BOLD response. Consistent with our pilot work, to enhance external validity and provide context for counselor utterances, we will present youth with clinical exchanges directly inspired by their Week 1 MI or BAM session. Specifically, 5 client change talk statements (CT; e.g., *"I've been blacking out lately"*) will be generated during the Week 1 MI or BAM session. Using the themes of these CT statements as a guide (e.g., references to getting in trouble, feeling hungover), the PI and study counselors will select pre-recorded (from the NILE pilot portion) MI-consistent statements (empathically inflected complex reflection; e.g., *"It is scary to see your drinking is starting to get out of control."*), BAM-consistent statements (e.g., *"You're noticing that your drinking is starting to change"*), and BAM- and MI-inconsistent statements (e.g., *"Your drinking is starting to get out of control"*). All counselor statements will be audio-recorded by the participant's study counselor for presentation within the NILE fMRI paradigm. In line with our successful pilot work ([name] et al under review-a), we will assess the strength of counselor language on youth's BOLD response. All participants receive one ~13 minute run of the NILE task, with order counterbalanced across participants. Each run will include 20 counselor statements of each type, for a total of 60 statements per NILE task version. Each run will consist of 60×12.5-second trials. Each trial will consist of one 500ms "listen" cue, one 4 second audio clip and visual text presentation of the counselor statement, and a 4-10 second fixation jitter necessary for modeling the BOLD response during analysis.

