Intervention Session 2. Immediately after the scan, youth will meet with their study counselor in a private visit room within OHSU. The second MI session focuses on providing youth personalized feedback regarding their alcohol use (from their baseline data), working with youth to identifying high-risk drinking situations, and determining avenues to help reduce their problem drinking (see Session 2 MI). The BAM group receives mindfulness problem-solving strategies to practice in daily life and in addition, the counselor will discuss the connection between anxiety, stress, and worry with alcohol use, and will reiterate mindfulness concepts. The second intervention sessions for both groups will be audiotaped, but there will be no videotaping as the fMRI stimuli comes from Intervention Session 1 and thus verification is only required for the first session.

Follow-Up Procedures. Given that the impact of MI on youth distal behavior change (>6 month) is not well understood (Jensen et al 2011, Larimer & Cronce 2007), we will evaluate youth over a 12-month period using a near-identical behavioral measurement package administered at baseline (specifically, at 3-, 6-, and 12-months) to obtain an understanding of the nature and duration of brain-based factors in youths' alcohol treatment response. Certain questionnaires will only be administered at Session 1 because they capture a "past year" period (DPS, CTQ) or do not require readministration throughout the entire study (Arrest and Recidivism History, Family Substance Use). The PDS will only be administered at scan visits (Session 2 and the 3 month follow up). See Measures List for additional details. At each in-person visit, we will have the participant complete a breathalyzer and urinalysis to corroborate self-report of drug and alcohol use. For the 3-month follow up, in addition to the follow up procedures described above, participants will return to OHSU for a final MRI scan identical to the one completed in Session 2, and complete the **TLFB 3 Day Use Short Form** before scanning to check for recent substance use. Consistent with our prior NIH- and IRB-approved protocols, 6- and 12-month follow-ups can be completed in-person at a location convenient for youth (e.g., community centers; OHSU), but will be offered to participants as a combination phone (for the TLFB interview) and REDCap (for the remaining measures)

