Sample size was selected to evaluate the primary research questions at a two-tailed alpha of .05 and power of .80. Estimates of effect size were conducted in G*Power 3 (Faul et al 2009, Faul et al 2007). For **Hypothesis 1**, the relationship between MI-consistent therapist statements and brain-based response, in our pilot evaluation, we found that MI-consistent behaviors (as contrasted with non-MI-consistent behaviors) showed a large effect size ($z = 2.27$, $d = 1.31$) within the IFG ([name] et al under review-a). Thus, this effect size requires a sample size of 22 subjects to power Hypothesis 1. In terms of **Hypothesis 2**, that brain activity will correlate with reductions in proximal and distal problem drinking, our pilot study showed significant relationships between MI-consistent therapist behaviors and proximal (1-month) reductions in binge drinking days (right IFG $z = 3.38$, $d = 1.95$; insula $z = 2.238$, $d = 1.29$) ([name] et al under review-a); thus, for this analysis, we would need 22 subjects to detect proximal behavior change. However, because no study to our knowledge has evaluated how BOLD response relates to youths' distal (12-month) behavior change, we suggest a more conservative (medium) effect size of $d = .70$ for this heretofore unexamined relationship. Together, this suggests the need for 68 youth to detect both proximal and distal behavior change for Hypothesis 2. For **Hypothesis 3** we refer to the work of Fritz and MacKinnon (2007) to determine sample size for our mediation hypothesis. For the A path, the relationship between therapist speech and adolescent BOLD response, our pilot evaluation suggests a large effect for MI-consistent therapist behaviors on BOLD activation. For the B path, the relationship between youth brain response and subsequent behavior change (proximal and distal treatment outcomes), we anticipate a medium effect size. For the indirect effect, that is, the effect of therapist speech upon problem drinking outcomes mediated by youth brain response, Fritz and MacKinnon indicate that with a large effect for the A path and a medium effect for the B path, we would need a sample of $N = 204$ to detect a mediated effect for Hypothesis 3 with power of .80 at an *a priori* alpha of .05.

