The Impact of Attrition. In our prior NIAAA R01 with drinking youth (PI [name]), we have an established track-record of retaining ~84% of adolescents at our most distal (12 month) follow-up. Thus, we project losing 16% of the proposed sample, thus requiring **N = 243** youth to account for attrition.

Analysis Plan.

Analyses will be conducted to evaluate (1) the relationship between therapist behavior and youth brain response (BOLD), (2) the relationship of youth brain response (BOLD) to changes in youth problem drinking across proximal (3- and 6-month) and distal (12-month) follow-ups, and (3) the mediational role of BOLD activation on the relationship between therapist behaviors and youth problem drinking outcomes. Measures will be derived from the baseline fMRI scan and behavioral data collected at baseline, 3-, 6- and 12-months.

fMRI preprocessing and single-subject analysis. The first three volumes of each run will be discarded to allow the MR signal to reach steady state. The remaining images in each youth's time series will be motion corrected (Jenkinson, Bannister, Brady, & Smith, 2002) using FSL's MCFLIRT module (FMRIB's Software Library). Images will be spatially smoothed with a 3D Gaussian kernel ($FWHM = 8 \text{ mm}^3$), intensity normalized and temporally filtered with a 50 sec high pass filter FEAT (FMRIB's Easy Analysis Tool) (Smith et al., 2004).

We will utilize a regression approach (GLM - general linear model) to extract regularities with regard to temporal aspects (i.e., time series) of the data. Statistical analysis will be carried out using FILM (FMRIB's Improved Linear Model) with local autocorrelation correction. We will create an explanatory variable (EV) for each trial type (MI-consistent, BAM-consistent, BAM- and MI-inconsistent). For each participant, we will use FILM to obtain a parameter estimate for each EV and create appropriate contrasts. Contrast maps of parameter estimates (PE) for each youth are transformed into a common stereotaxic space using the following 2-step registration prior to the group analyses. Statistical maps will be warped into the common MNI stereotaxic space (Jenkinson et al., 2002) before a random effect group analysis is performed. To do so, (1) the EPI image will be registered to the participant's high resolution T1 weighted image; (2) the T1-weighted high resolution image will be registered to the MNI 152 brain template image; and (3) statistical images

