will be transformed to MNI space using the transformations matrices from step 2. Coordinates will be reported in MNI space. All registration will use FNIRT (FMRIB's Nonlinear Image Registration Tool).

To test **Hypothesis 1**, that MI-consistent therapist behaviors will be associated with greater BOLD response (MFG, IFG, insula) than MI-inconsistent therapist behaviors, we will utilize the same procedure used in our pilot study ([name] et al under review-a). Group-level activations will be evaluated for MI-consistent vs. MI-inconsistent for change talk (CT) and sustain talk (ST) separately across the whole brain and thresholded using a false discovery rate (FDR) set to a false-positive $p < 0.05$. Following our prior work ([name] et al under review-a, [name] et al 2013b), to test **Hypothesis 2a** (from original submission), that BOLD response will be directly associated with proximal (3-, 6-month) and distal (12-month) behavior change (reductions in youth problem drinking), we will utilize an index of youth problem drinking (past month binge drinking days; derived from TLFB + past month alcohol-related problems; derived from RAPI). We will conduct linear regression analyses in FSL with baseline measures of alcohol use behavior and alcohol problems included as regressors to assess correlations between BOLD response and behavior change for youth problem drinking at each follow-up time point. To test **Hypothesis 2b** of the Supplement, that greater BOLD response will be directly associated with proximal (3-, 6-month) and distal (12-month) behavior change (reductions in youth cannabis use), we will utilize an index of youth problem cannabis use (past month cannabis use days; derived from TLFB + past month cannabis related problems; derived from Cannabis Problems Questionnaire). We will conduct linear regression analyses in FSL with baseline measures of cannabis use behavior and cannabis problems included as regressors to assess correlations between BOLD response and behavior change for youth problem cannabis use at each follow-up time point.

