To test **Hypothesis 3a** (from original submission) and 3 b (from supplement) that BOLD response (MFG, IFG, insula) will mediate the relationship between therapist behaviors (MI-consistent) and proximal and distal reductions in youth problem substance use (drinking; cannabis use), we will use the product of coefficients method (Sobel 1982). Because the distribution of the product of coefficients is typically not normal, we will apply appropriate asymptotic confidence limits (MacKinnon et al 2007) following Co-I [name]'s prior work examining causal chains in MI (Moyers et al 2009). Coefficients and standard errors for the A and B paths will be computed in FSL using the variables from Hypotheses 1 and 2 (i.e. signal change difference between MI-consistent and MI-inconsistent language, with (a) past month binge drinking/alcohol-related problems at 3-, 6- and 12-months; (b) past month cannabis use/cannabis-related problems at 3-, 6- and 12- months), and tested using the PRODCLIN macro (MacKinnon et al 2007). We will perform separate tests for proximal and distal drinking, each tested at $\alpha = .05$.

9) Privacy, Confidentiality and Data Security

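### The Hypothesis 3 product of coefficients cannot test mediation: the type of statement heard in the scanner is the same for every participant, so no effect of therapist language on drinking is estimated

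*Combined protocol and SAP*

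**What the plan says.** Section 2 gives Hypothesis 3, the only one under Aim 2, in these words: "BOLD response (MFG, IFG, insula) will mediate the relationship between MI-consistent therapist behaviors (e.g., reflections) and proximal and distal reductions in adolescent problem drinking". Section 8, Analysis Plan, tests it by the product of coefficients with PRODCLIN limits, separately for proximal and distal outcomes, each at .05. On the paths it says: "Coefficients and standard errors for the A and B paths will be computed in FSL using the variables from Hypotheses 1 and 2". It names those variables as the signal-change difference between MI-consistent and MI-inconsistent language, and drinking (3a) or cannabis (3b) measures at 3, 6 and 12 months.

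The pieces that feed this are:

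- **Exposure** (section 6, NILE fMRI Task): "Each run will include 20 counselor statements of each type, for a total of 60 statements per NILE task version". Participants in both arms do the task. In section 8, statement type is a trial-level regressor in each participant's own model.
- **B path** (section 8, Hypothesis 2a): linear regressions "with baseline measures of alcohol use behavior and alcohol problems included as regressors to assess correlations between BOLD response and behavior change", at each follow-up.
- **Data used** (section 8): "Measures will be derived from the baseline fMRI scan and behavioral data collected at baseline, 3-, 6- and 12-months".
- **Power** (section 8, Hypothesis 3): "with a large effect for the A path and a medium effect for the B path, we would need a sample of" 204, raised to 243 for 16% attrition.
- **Arm** (section 6, Control Condition and Rationale): youth are randomised half to MI and half to BAM, and the plan says MI cannot be evaluated without a comparison condition. Arm is not a term in any model for Hypotheses 1 to 3.

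**The concern.** A mediation analysis needs an exposure that varies across the units on which the outcome is measured. Here the exposure varies only between trials inside one scan, while the outcome varies only between people. Drinking at 3, 6 or 12 months cannot be divided into a part that followed MI-consistent statements and a part that followed the others. A within-person mediation model is therefore not available either.

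What remains is a product of two quantities that do not form a chain. If youth with a larger contrast drink less for any reason, including a stable trait, and the mean contrast is not zero, the product is significant and would be reported as brain response mediating the effect of therapist language. Section 3 (Significance) says that such a result would lead the team to modify its adolescent MI protocol and disseminate it, so the label on the result matters.

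**Working it through.** **1. The plan's own figures.** 204 / (1 - 0.16) = 242.9, so 243 reproduces. The 204 comes from a cited source and cannot be checked from the documents. The Hypothesis 1 size of 22 reproduces at d = 1.31 only as a two-independent-group t test (power .83); a paired test at that d would need 7. The Hypothesis 2 size of 68 reproduces in the same way at d = .70 (power .81). The Hypothesis 1 sizing thus treats statement type as a between-person factor, although the task makes it within-person.

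**2. What A and B are.** Let D be one participant's MI-consistent minus MI-inconsistent contrast and Y that participant's drinking at a follow-up.

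- A = mean of D over participants, which is the Hypothesis 1 quantity.
- B = slope of Y on D, adjusted for baseline, which is the Hypothesis 2 quantity.
- An effect of X (statement type) on Y would need X to vary between participants. It does not: var(X) = 0, and a design matrix holding an intercept and X has rank 1, so no total or direct effect can be fitted.

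**3. How the test behaves.** Simulated trials had N = 204 (102 per arm), no arm effect and no effect of BOLD on drinking. D = mean + trait + noise; Y = trait + baseline + noise. Product limits came from 3,000 Monte Carlo draws, with 2,000 trials per scenario (standard error at most 1.1 points). Inputs:

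- A-path d = 1.31: the pilot IFG value in section 8.
- A-path 0.655: an assumption. Pilot n is not stated, but d = 2z/√n gives n = 12 for all three pilot pairs (2.27/1.31, 3.38/1.95, 2.238/1.29), hence 2.27/√12 = 0.655.
- A-path 0.2 and 0.1: assumptions, because the plan gives no A-path size for MFG or insula.
- Correlation of D with Y: r = .33 from the plan's d = .70, by .70/√(.70² + 4); r = .20 is an assumed lower value; r = 0 is the null.

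Percentage of trials significant:

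| A-path d | r | H1 | H2 | H1 and H2 | H3 product |
|---|---|---|---|---|---|
| 1.31 | .33 | 100 | 99.6 | 99.6 | 99.6 |
| 1.31 | .20 | 100 | 81.4 | 81.4 | 82.0 |
| 1.31 | 0 | 100 | 5.0 | 5.0 | 5.4 |
| 0.655 | .33 | 100 | 99.8 | 99.8 | 99.8 |
| 0.655 | .20 | 100 | 82.3 | 82.3 | 82.6 |
| 0.655 | 0 | 100 | 4.4 | 4.4 | 4.4 |
| 0.2 | .33 | 81.6 | 99.8 | 81.4 | 82.0 |
| 0.2 | .20 | 81.2 | 82.7 | 66.8 | 65.0 |
| 0.2 | 0 | 81.4 | 5.6 | 4.4 | 4.0 |
| 0.1 | .33 | 29.5 | 99.7 | 29.4 | 29.8 |
| 0.1 | .20 | 31.6 | 81.9 | 26.4 | 24.8 |
| 0.1 | 0 | 29.0 | 4.5 | 1.1 | 0.8 |

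With A at 1.31 and r of .20 or .33, the Hypothesis 3 and Hypothesis 2 decisions agreed in 98.5% to 99.9% of trials. Where A is weak, the product follows the joint significance of Hypotheses 1 and 2.

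**4. The same world with arm as exposure.** Trait-only link, arm included in the B model:

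| Arm difference in contrast, d | Declared at r = .20 | Declared at r = .33 | A-path power, 102 per arm |
|---|---|---|---|
| 0 | 3.6% | 4.6% | - |
| 0.2 | 21.9% | 28.3% | 29.5% |
| 0.4 | 65.6% | 80.9% | 81.1% |
| 0.5 | 75.6% | 93.8% | 94.5% |

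**The case against.** The strongest reply is that the 82% and 99.6% are simply Hypothesis 2 power at an assumed r, and that confounding of mediator and outcome troubles any mediator that is not randomised, including an arm-based analysis (66% to 81% at arm d = 0.4). It stands that the percentages depend on r and that the core defect is logical and needs no simulation. The reply does not remove the defect. In the same trials with no arm effect, the arm-based test is positive in about 4% to 5% and the written test in 82% to 99.6%, because the written A path is a mean response and not an effect of an exposure that differs between people.

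Other points:

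- Hypothesis 1 is whole-brain with FDR control, and the plan does not say which regional summary enters PRODCLIN. The simulation uses one scalar contrast, so the equivalence with Hypotheses 1 and 2 is close but not exact. This stands as a qualification.
- Statement content is individualised. But the count of each type is fixed, and only type enters the contrast.
- The error rate is controlled when BOLD does not predict drinking, and Hypotheses 1 and 2 remain interpretable. Both are true. The harm is to the claim made under Aim 2 and to the basis for N.
- Section 2 still describes all 243 youth receiving MI, so the analysis text may predate the two-arm design. That would explain the omission of arm but does not supply an exposure.

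**Conclusion.** The concern holds and should be fixed before analysis. As written, Hypothesis 3 contains no effect of therapist language on drinking, and no other section supplies an exposure that differs between people. This conclusion rests on the design alone and needs no assumed effect size.

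The practical size does rest on assumptions: a scalar contrast, r of .20 to .33, and A-path sizes other than the IFG value. On those, an association with no causal content would be called mediation in 82% to 99.6% of trials at the plan's IFG effect, 65% to 82% at d = 0.2 and 25% to 30% at d = 0.1. The same defect applies to the cannabis version, Hypothesis 3b. The 243 follows arithmetically from 204, but 204 was chosen for an indirect effect that this analysis does not estimate.

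**What to change.** **Option (a), the cheaper.** Drop the mediation claim for the statement-type contrast. Report Hypothesis 1 as a within-scan effect and Hypothesis 2 as a baseline-adjusted association. This changes SAP wording only, on data already planned. The cost is the loss of the mediation claim and the need for another justification of 204.

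**Option (b), if mediation is kept.** Set X = randomised arm, M = the Session 2 scan contrast and Y = follow-up problem drinking adjusted for baseline. Include arm in the B-path model, report the direct effect and keep the PRODCLIN limits. The SAP must then state four things:

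1. M is not randomised. Randomisation protects the A path only, and B assumes no unmeasured confounding of M and Y. Add a sensitivity analysis giving the residual M-Y correlation at which A × B becomes zero.
2. M reflects Session 1 only, since the scan precedes Session 2: "Immediately after the scan, youth will meet with their study counselor in a private visit room within OHSU".
3. BAM is an active comparator that also addresses drinking (in its second session, "the counselor will discuss the connection between anxiety, stress, and worry with alcohol use"), so X is MI versus BAM and not therapy versus none.
4. The power statement for 204 no longer applies.

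Option (b) changes the hypothesis from statement type to arm, and no section predicts an arm difference on this contrast. Completers for 80% power (A-path power × B-path power), with enrolment at 16% attrition:

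| Arm d | r | Completers | Enrolled (completers / 0.84) |
|---|---|---|---|
| 0.4 | .33 | 200 | 239 |
| 0.5 | .20 | 212 | 253 |
| 0.4 | .20 | 256 | 305 |
| 0.3 | .20 | 372 | 443 |

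At 204 completers, power is about 66% for d = 0.4 and r = .20. Option (b) is also only a partial cure: if arm shifts BOLD, a trait-only link still yields declared mediation at the rates in the arm table above.

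Two other sources could be considered. The 3-month scan follows both sessions and precedes the 6- and 12-month outcomes, but it will be missing for youth who complete that visit remotely. Coded in-session therapist behaviour is closer to the wording of Hypothesis 3, but it is not randomised, and only 25% of recordings are now due to be evaluated, for fidelity.

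### As written, the Hypothesis 3 B path comes from an FSL model that implies BOLD as the response, so A × B and its PRODCLIN limits would not estimate the mediated effect on drinking

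*Combined protocol and SAP*

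**What the plan says.** All of the relevant text is in section 8 (Data Analysis) of the combined protocol and SAP.

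- **Hypothesis 3.** Mediation is assessed by the product of coefficients, with limits that allow for the non-normal distribution of the product. "Coefficients and standard errors for the A and B paths will be computed in FSL using the variables from Hypotheses 1 and 2". The variables are described as "signal change difference between MI-consistent and MI-inconsistent language, with (a) past month binge drinking/alcohol-related problems at 3-, 6- and 12-months". The coefficients then go to PRODCLIN, with separate 5% tests for proximal and distal drinking. The same wording covers the cannabis mediation (3b).
- **Hypothesis 2a**, which supplies B: "We will conduct linear regression analyses in FSL with baseline measures of alcohol use behavior and alcohol problems included as regressors to assess correlations". These analyses relate BOLD to behavior change at each follow-up. The response variable is not named.
- **fMRI preprocessing and single-subject analysis.** "For each participant, we will use FILM to obtain a parameter estimate for each EV and create appropriate contrasts". For the group stage: "Statistical maps will be warped into the common MNI stereotaxic space", after which a random-effects group analysis is run.
- **Power analysis.** "For the B path, the relationship between youth brain response and subsequent behavior change (proximal and distal treatment outcomes), we anticipate a medium effect size". The indirect effect is defined there as the effect of therapist speech on problem drinking, carried by brain response.

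**The concern.** A product of coefficients estimates an effect on drinking only if the last link is a regression of drinking on the mediator. The plan takes that link from FSL, and in the only FSL model that it spells out the image is the quantity being explained. If the group regression follows the same pattern, B is the slope of BOLD on drinking, the reverse of the B path in the power section. PRODCLIN would then return limits for a quantity that is not the mediated effect.

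This matters because Hypothesis 3 is the whole of Aim 2 and sets the sample size. The plan also promises confidence limits for the product. The Background (Significance) says that a mediation finding would be used to modify the MI treatment protocol, so the size of the effect will be read as well as whether it differs from zero.

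**Working it through.** **1. The plan's own figure.** The Hypothesis 3 size is 204, and 204 / (1 − 0.16) = 242.86, which rounds up to 243, as stated. The 204 rests on a cited table that the documents do not reproduce, so it was not checked. Nothing below changes the sample size.

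**2. The passages side by side.**
- The power section runs from BOLD (predictor) to drinking (response).
- The single-subject FSL model has the image time series as response and trial types as predictors.
- The group FSL model takes contrast maps as input. Its response is not stated, and image-as-response is the natural continuation.
- Hypothesis 2a names only the baseline drinking measures as regressors and does not say on which side follow-up drinking stands.
- No passage describes taking one BOLD value per youth and using it to predict drinking.

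**3. Units.** Let A be the mean MI-consistent minus MI-inconsistent signal change, in BOLD units.
- Drinking as response: B is in drinking units per BOLD unit, so A × B is in drinking units.
- BOLD as response: B is in BOLD units per drinking unit, so A × B is in BOLD-squared per drinking unit.

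**4. Algebra.** With the same covariates in both least-squares models:

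reversed B / forward B = Var(BOLD | covariates) / Var(drinking | covariates) = k

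The t statistic depends only on the partial correlation and the degrees of freedom, so it is the same in both directions. The standard error is therefore also multiplied by k. The product limits are the forward limits times k, and k is positive, so whether they exclude zero does not change.

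**5. Illustration.** The documents give no SDs or correlations, so these are assumptions: n = 204, generating partial correlation −0.3, one simulated data set per row, baseline drinking as covariate. The limits come from 1,000,000 draws of the product of two independent normals, the distribution that PRODCLIN targets.

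| SD BOLD | SD drinking | Baseline correlation | Forward B | Reversed B | k | t (both) |
|---|---|---|---|---|---|---|
| 0.3 | 4 | 0.5 | −4.4179 | −0.0341 | 0.0077 | −5.97 |
| 0.15 | 4 | 0.5 | −5.6482 | −0.0092 | 0.0016 | −3.32 |
| 1 | 4 | 0.5 | −0.9675 | −0.0879 | 0.091 | −4.32 |
| 0.3 | 8 | 0.5 | −7.0945 | −0.0157 | 0.0022 | −5.02 |
| 1 | 1 | 0.5 | −0.2684 | −0.3424 | 1.28 | −4.51 |
| 1 | 1 | 0.7 | −0.2404 | −0.4395 | 1.83 | −4.87 |

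For the first row, the algebra predicts k = 0.3² / (4² × (1 − 0.5²)) = 0.09 / 12 = 0.0075, against 0.0077 in the sample. A is −0.686 / −4.4179 = 0.155.
- Forward: A × B = −0.69 days, 95% limits −0.99 to −0.42.
- Reversed: A × B = −0.0053 BOLD-squared per day, 95% limits −0.0077 to −0.0032.

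The last two rows show that giving both variables an SD of 1 does not remove the difference, because baseline drinking explains part of the variance of drinking and not of BOLD.

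**The case against.** The strongest reply is that the reversed direction is nowhere written down. The explicit image-as-response model is the single-subject one. Baseline adjustment, which is all that Hypothesis 2a specifies, fits equally well with follow-up drinking as the response. The Objectives speak of BOLD predicting behavior, and the signal change difference in Hypothesis 3 could mean one extracted value per youth. This stands to the extent that the direction is an inference from the FSL workflow, and the point must be worded that way. It does not remove the point. The plan commits to FSL coefficients and standard errors for both paths, describes no extraction step, and leaves the response unnamed in the model behind Aim 2.

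The second reply is that the plan frames Hypothesis 3 as a test, and the test survives. That is right under identical covariates. A reader might infer that the mediation test is invalid or the study mis-sized; the documents do not support either. But the plan also commits to confidence limits, and those would be for the wrong quantity.

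A reader might also take k as the factor by which the effect is mis-stated. It compares slopes in different units and moves with the assumed SDs, so it is not a measure of bias. Nor are days certain to be the final unit: Hypothesis 2a describes an index that combines binge days and alcohol-related problems.

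**Conclusion.** The point holds in a conditional form. Followed literally, the FSL route implies a B coefficient in BOLD per unit of drinking, opposite to the B path in the power section. A × B and its PRODCLIN limits would then not estimate the mediated effect on drinking. The error lies in the estimate, its units and its limits. With the same covariates and ordinary least squares, the B-path t and the exclusion of zero at the 5% level are the same in either direction. That equality would fail if the two models carried different covariates.

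The conclusion rests on reading the group model as a continuation of the described FSL workflow. This is a strong inference, not a statement in the plan. The numerical illustration rests on assumed SDs and correlations and shows the mechanism only. The plan should be corrected before analysis; the sample size and data collection are unaffected.

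**What to change.** State in the Hypothesis 3 text that follow-up problem drinking is the response in the B-path model. Then:

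1. Extract each youth's mean MI-consistent minus MI-inconsistent signal change in predefined MFG, IFG and insula masks.
2. Regress follow-up drinking on that value together with the baseline drinking measures.
3. Add the exposure only if it varies between participants and is the same exposure as in the A path. The NILE task gives every participant 20 statements of each type, so the language contrast is within-person. Treatment arm would be a different exposure and would need an A path to match.
4. Pass that slope and standard error to PRODCLIN.
5. Do the same for the cannabis mediation (3b), with cannabis use as the response and baseline cannabis measures as covariates.

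The voxelwise FSL maps stay as planned for Hypotheses 1 and 2. The cost is a few sentences in the plan, one extraction step, and the loss of voxel-level detail in the mediation model.
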